Correlate the degree of satisfaction of the patients with several clinical-demographic variables, including: age, marital status, diagnosis, comorbidities, symptomatology.

4. Hypotheses

Hypothesis 1: most patients will be satisfied without the presence of a chaperone during the anorectal examination.

Hypothesis 2: Most patients will be dissatisfied without the presence of a chaperone during the anorectal examination.

5. Materials and Methods

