5.1 Study population

Adult women (18 years of age or older) who present for an initial consultation at our Coloproctology Division will be studied. These patients will be randomized into two groups:

- 1- Patients undergoing proctological examination with the presence of a chaperone.
- 2- Patients undergoing proctological examination without the presence of a chaperone.

The chaperone will always be a female, and may be a nurse or nursing assistant. Her participation will be communicated to the patient, who must agree to her presence during the proctological examination. After the consultation is completed, the patient will be informed that a study is being conducted and, if she agrees to participate, she should answer a specific questionnaire regarding the physical examination that was just performed. The purpose of the study will be explained, as well as the fact that participation is voluntary, not will change her clinical management, being guaranteed the secrecy and inviolability of the information obtained.

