5.3. Primary Outcome Measure

The main outcome to be assessed will be patients' preference regarding the presence of a female chaperone during anorectal examination. It will also be assessed the degree of comfort (or embarrassment) according to the presence or not of a female chaperone during the proctological exam. This will be measured through a questionnaire compound of 6 questions (see Annexes 1 and 2). Each question will provide a isolated result (there will be no total score). The questions are the following:

1. How did you feel during the exam?
Patients will register their answer in a scale from zero (completely embarrassed) to 10 (completely comfortable)
2. What did you think of (not) having a person besides the doctor during the exam?
Patients will have 3 possible answers: bad, indifferent, good.
3. Would you rather have taken the exam in the (without) presence of another person (woman)?
There are 3 possible answers: yes, no, indifferent.
4. Do you think the (absence) presence of another person made the examination:

There are 3 possible answers: better, worse, did not change it.

5. Did you feel more (less) protected with (without) the presence of another person?

There are 3 possible answers: yes, no, indifferent.

6. In the event of a reexamination, would you want another person's presence again?

There are 3 possible answers: yes, no, indifferent.

Or: Would you again like the doctor to examine you without another person's presence?

There are 3 possible answers: yes, no, indifferent.

6. Ethical aspects

This research project follows the Normative Resolution 01/97 of the Commission for Research and Ethics in Health, as part of the Research Group and Post-graduation Program/ HCPA. There will be no change in medical investigation and management whether or not the patient decides to participate in the study. The researchers guarantee to preserve the privacy of patients whose data will be collected, to use this information solely and exclusively for the execution of this project and to publish the information obtained only anonymously.

7. Budget and sources of funding

There will be no additional cost to the HCPA with the completion of the study. The computer equipment and software required for data recording and its subsequent analysis are already available at our Division, and there is no need for new acquisitions or financing.

8. Sample size

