The sample size was calculated based on a study conducted by Teague et al. (9), which showed that a larger number of women is more comfortable with the presence of a chaperone if the examining physician was a man, compared to the situation in which the examination was conducted by a female physician (31% vs. 14%, $P < 0.01$) (9). Using these differences, with 90% power and 0.05 error was estimated through the SPSS program, it would be required a total of 94 patients in each study group (with or without companion). Considering the volume of first visits attended in our Division of Coloproctology, it is estimated that the data collection will be completed in approximately two years.

9. Statistical Analysis Plan

Categorical variables will be described by absolute and relative frequency (percentage). The quantitative variables with symmetrical distribution will be described by the mean and standard deviation.

Quantitative variables with asymmetric distribution will be described by median and interquartile range (percentiles 25 and 75). Chi-square or Chi-square tests with Yates correction will be used to compare the categorical variables. Quantitative variables with symmetrical distribution will be compared by the Student t test for independent samples. Quantitative variables with asymmetric distribution will be compared by the Mann-Whitney test. A level of statistical significance of 5% shall be considered in all tests used.

10. Cronogram of Activities

Date	Activities
January and February 2018	Elaboration, submission and approval of the research project
July 2018 to July 2020	Data collect
August to September 2020	Statistical analysis
October 2020	Bibliographic review and elaboration of the scientific article

12. References

- 1- The Royal College of Obstetricians and Gynaecologists. Gynaecological examinations, guidelines for specialist practice. London: RCOG, 2002.
- 2- Intimate Examinations. London, UK, General Medical Council. December 2001.
- 3- Gawande A: Naked. *N Engl J Med* 2005, 353(7):645-648.
- 5- College of Physicians and Surgeons of Ontario: Avoid complaints of sexual abuse (policy document) [<http://www.cpso.on.ca/Policies/avoid.htm>].

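### Prespecifying baseline adjustment for the 0–10 comfort score (question 1) would be a cheap gain in precision; the planned unadjusted comparison is valid but may give some up

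*Combined protocol and SAP*

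**What the plan says.** Section 9 assigns a test by type of variable. Categorical variables get a chi-square test, with or without Yates correction. For quantitative variables, "Quantitative variables with symmetrical distribution will be compared by the Student t test for independent samples", and the Mann-Whitney test is used when the distribution is asymmetric. It adds that "A level of statistical significance of 5% shall be considered in all tests used". It names no regression model, covariate, effect estimate or confidence interval.

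Section 5.3 states that "The main outcome to be assessed will be patients' preference regarding the presence of a female chaperone during anorectal examination" and adds the degree of comfort as a further outcome. Comfort is question 1: "Patients will register their answer in a scale from zero (completely embarrassed) to 10 (completely comfortable"). The remaining five questions have three answer categories, although Annex 2 also prints 0, 5 and 10 under question 2.

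Section 3.2 sets the aim of correlating satisfaction with clinical and demographic variables, "including: age, marital status, diagnosis, comorbidities, symptomatology". Section 5.1 says "These patients will be randomized into two groups" and names no stratification factor. Section 8 gives the size: "it would be required a total of 94 patients in each study group".

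**The concern.** Age, marital status and presenting symptoms could plausibly be related to how embarrassed a woman feels during an anorectal examination. If they are, their contribution stays in the residual variance of a two-sample comparison and widens the interval around the chaperone effect on question 1. Objective 3.2 requires these variables anyway, so the adjustment would cost only analysis time.

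At stake is some power and interval width on one listed outcome. The validity of the comparison is not in question. The point concerns the comparison between arms, not the method for estimating the associations in objective 3.2.

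**Working it through.** **Inputs from the documents.** 94 women per group, 188 in total, taking allocation as equal (section 8); significance level 5% (section 9), taken as two-sided because sidedness is not stated; planning rates 31% and 14% with 90% power (section 8).

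**Assumptions, because the documents give nothing.** R² is the share of within-arm variance in question 1 explained by the covariates. k is the number of covariate terms, set at 5 (age as one term, plus a few category indicators for marital status and presenting symptom). No standard deviation is given, so effects are in SD units.

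**Step 1: the plan's own figure, to choose a baseline.** With pooled variance, n per group = [1.960·√(2·0.225·0.775) + z_power·√(0.31·0.69 + 0.14·0.86)]² / 0.17².
- 90% power (z = 1.282): n = 125.
- 80% power (z = 0.842): n = 94.

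The stated 94 is reproduced at 80% power, not at the stated 90%; power at 94 per group is 80.2%. This calculation is for proportions, and question 1 was not sized. An 80% baseline is therefore an assumption, in line with what 94 per group delivers. A 90% baseline is shown as well.

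**Step 2: the unadjusted reference effect.** d = √2·(1.960 + z_power)/√94, which is 0.409 SD for 80% power and 0.473 SD for 90%.

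**Step 3: adjustment, charging for the covariate terms.** The ratio of adjusted to unadjusted standard error is r = √{(1 − R²)·[1 + k/(N − k − 3)]}. With N = 188 and k = 5 the bracket is 1 + 5/180 = 1.028. Effective n per arm is 94/r². Power is Φ(2.802/r − 1.960) from the 80% baseline, with 2.802 = 1.960 + 0.842.

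| Assumed R² | SE ratio r | Effective n per arm | Power from 80% | Power from 90% |
|---|---|---|---|---|
| 0 | 1.014 | 91.5 | 78.9% | 89.2% |
| 0.02 | 1.004 | 93.3 | 79.7% | 89.8% |
| 0.05 | 0.988 | 96.3 | 80.9% | 90.7% |
| 0.10 | 0.962 | 101.6 | 83.0% | 92.1% |
| 0.20 | 0.907 | 114.3 | 87.1% | 94.7% |

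Break-even is where (1 − R²)·(185/180) = 1, that is R² = 5/185 = 0.027. With k = 8, power from the 80% baseline is 78.2% at R² = 0 and 80.3% at R² = 0.05, which is why the covariate list should be short.

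**Step 4: can the same model be used for the preference items?** Set the two arms' wordings in section 5.3 side by side, with Annex 2 confirming the no-chaperone version:
- Question 3: *yes* means she would rather have been examined without another person in the chaperone arm, and with one in the other arm.
- Question 6: *yes* means she wants a chaperone next time in the chaperone arm, and wants none in the other arm.

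A model of raw yes against not-yes would compare answers to opposite questions. Question 1 is worded identically in both arms and has no such problem.

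**The case against.** The strongest reply is that nothing here is wrong. In a randomised comparison the unadjusted test is valid, and its standard error already allows for chance imbalance. At 94 per arm a covariate's between-arm difference has SD √(2/94) = 0.146 SD units, so a gap above 0.2 SD occurs about 17% of the time. That is ordinary sampling variability, not bias. This stands, and it makes the point an efficiency suggestion.

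Three further objections also stand.
- A reader might infer from objective 3.2 that the investigators expect these variables to drive satisfaction. Section 3.2 only sets a correlation aim, and neither hypothesis in section 4 mentions a covariate. That the variables will be available for every woman is likewise inferred from the aim; no data form in the text lists them.
- A reader might conclude that free precision is being thrown away. Using 1 − R² alone, with no charge for covariate terms, gives 82%, 84% and 88% power at R² of 0.05, 0.10 and 0.20. Charging for 5 terms lowers these by about 1 point, and below R² of about 0.03 there is no gain. Nothing in the documents says where R² lies.
- The main outcome is preference, and section 8 sizes the trial on proportions. The figures above are normal-theory results for a mean difference. They do not carry over to the chi-square comparisons, or to the Mann-Whitney test if question 1 is asymmetric.

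What remains is that the possible loss is about 1 point of power, the possible gain is several points, and no new data are required. The adjusted analysis would also supply an effect estimate and interval, which section 9 does not name.

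**Conclusion.** The point holds as a cheap improvement limited to question 1. The planned comparison is unadjusted and valid, but it may give up precision that variables required by objective 3.2 could provide. Against an unadjusted 80%, the change in power runs from about −1 point (R² = 0) through +1 (0.05) and +3 (0.10) to +7 (0.20). From a 90% baseline the range is about −1 to +5 points.

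These figures assume two-sided 5%, 94 analysed per arm, 5 covariate terms, and a linear model for the mean score. R² and the number of terms are assumptions. The documents do not support reading this as an error in the analysis, as a demonstrated loss, or as a finding about the main preference outcome.

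**What to change.** Before the data are analysed, add to section 9 for question 1:
- The estimate is the adjusted mean difference between arms with its 95% confidence interval, from a linear model with arm, age (continuous), marital status (few categories) and presenting symptom (few categories). Use robust standard errors if the scores are skewed.
- Covariates are limited to variables fixed before the examination. The diagnosis made during it is not used.
- The unadjusted result is reported beside the adjusted one.

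State the category groupings in advance, and keep to about 5 terms in all.

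Do not apply the model to questions 3 and 6 as raw yes/not-yes answers. These would first have to be recoded to a common direction (wants a chaperone).

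The cost is a short paragraph in section 9 and a little more analysis, with no extra recruitment. The data needed are those that objective 3.2 already requires. If the covariates explain nothing, the price is about 1 point of power.

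### Six separately reported items share the primary outcome and every test runs at an unadjusted 5%: if all six are compared between arms, the chance of at least one false positive is about 11% to 26.5%

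*Combined protocol and SAP*

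**What the plan says.** Under the heading "5.3. Primary Outcome Measure", the protocol names as its main outcome the patients' "preference regarding the presence of a female chaperone during anorectal examination". The next sentence adds a second construct: "It will also be assessed the degree of comfort (or embarrassment) according to the presence or not of a female chaperone during the proctological exam". For the instrument it says: "This will be measured through a questionnaire compound of 6 questions (see Annexes 1 and 2". On reporting it says: "Each question will provide a isolated result (there will be no total score". No item is named as the primary one, and items 3 and 6 both ask about preference.

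Section 9 assigns tests by type of variable. For categorical answers: "Chi-square or Chi-square tests with Yates correction will be used to compare the categorical variables". Scores get a t test or a Mann-Whitney test. The error rule is a single sentence: "A level of statistical significance of 5% shall be considered in all tests used". Neither section gives an order of testing, an adjustment, or an exploratory label for any analysis.

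Section 3.2 adds a further set of tests: "Correlate the degree of satisfaction of the patients with several clinical-demographic variables, including: age, marital status, diagnosis, comorbidities, symptomatology".

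Section 8 sizes the trial on one comparison of two proportions, 31% against 14%, at an error of 0.05. It does not say which item that comparison stands for.

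**The concern.** The sample size assumes one test at 5%, while the analysis plan permits at least six under the primary outcome. With no item singled out, a significant result on any of them could be presented as evidence on the main question, and nothing in the plan would mark it as one result out of six. The associations with patient characteristics raise the same problem, since they fall under the same 5% rule.

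This matters more than it would in a well-studied field. Sections 1 and 2 say that no guideline and no study of patients' views exist for the proctological examination, and section 1 points to practical and legal consequences. A chance result on one item could become the reference finding.

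**Working it through.** **Inputs.** Six items, each reported separately (section 5.3). Level 0.05 for every test, no adjustment (section 9). Five named variables (section 3.2). 94 patients per group and rates of 31% and 14% (section 8). Sidedness is not stated; two-sided is assumed.

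**The plan's own figure.** The documents state no familywise error rate. The nearest figure is the 94 per group, which rests on a single test. The pooled two-proportion formula is

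n = [z(α/2)·√(2p̄q̄) + z(power)·√(p₁q₁ + p₂q₂)]² / (p₁ − p₂)²

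with p̄ = 0.225, √(2p̄q̄) = 0.5906, √(p₁q₁ + p₂q₂) = 0.5782 and (0.17)² = 0.0289.

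- 90% power: (1.960 × 0.5906 + 1.282 × 0.5782)² / 0.0289 gives 125.
- 80% power: (1.960 × 0.5906 + 0.842 × 0.5782)² / 0.0289 gives 94.

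So 94 matches 80% power, not the stated 90%. That is a separate matter and does not affect the error rates below.

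**Six items, no true effect.**

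- Independent tests: 1 − 0.95⁶ = 1 − 0.735 = 0.265.
- Bound that needs no assumption about dependence: 6 × 0.05 = 0.30.
- Correlated tests, simulated as six equally correlated two-sided normal statistics (400,000 draws):

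| Correlation | P(at least one significant) |
|---|---|
| 0.3 | 24% |
| 0.5 | 21% |
| 0.7 | 16% |
| 0.9 | 11% |

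Items 2 to 6 have three answer categories, so the normal model is an approximation for the correlated cases.

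**Preference items only.** If only items 3 and 6 were tested: 1 − 0.95² = 0.0975 if independent.

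**Covariate associations.** Section 3.2 speaks of satisfaction in the singular. One measure against five variables is 5 tests: 5 × 0.05 = 0.25 false positives expected, and 1 − 0.95⁵ = 0.226 for at least one if independent. The count rises if several items are used as satisfaction measures.

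**What a plain Bonferroni correction would cost.** With all six items co-primary at 0.05/6 = 0.0083, 94 per group gives about 56% power for 31% against 14%, and 90% power would need 183 per group. Naming one test is much cheaper.

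**The case against.** Four arguments on the other side carry weight.

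- **The outcome is partly ranked.** Section 5.3 calls preference the main outcome, so a reader who takes the six items as wholly unranked goes too far. But the ranking is between constructs. No item is named, two items ask about preference, and all six stay under the primary heading.
- **No rule says that one item is enough.** A reader might infer that a single significant item will be declared a positive trial. The documents do not say this. Reporting each question on its own supports item-by-item claims, and the hypotheses in section 4 concern what most patients feel, which is a descriptive question. What stands is that the plan does not prevent such a claim.
- **Six valid 5% tests are not actually defined.** Items 2 to 6 are worded in mirror form by arm: for example, item 5 asks about feeling more protected in one arm and less protected in the other. Raw answers can differ because the questions differ. The 26.5% therefore assumes that the answers have first been put on a common footing. Adjusting p-values does not repair a comparison that lacks this step.
- **Answers from one patient are correlated.** The real rate is probably below 26.5%. At a correlation of 0.9 it is still about twice 5%.

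A reader might also cross five variables with six items and get 30 tests, 1.5 expected false positives and 1 − 0.95³⁰ = 79%. Section 3.2 does not support that count: it names one degree of satisfaction and does not say that every item is used. Even with 30 tests, 79% needs full independence. Taking the six-item rates above and independent variables, 1 − (1 − p)⁵ gives about 69%, 59% and 44% at correlations of 0.5, 0.7 and 0.9.

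**Conclusion.** The point holds. As written, the plan allows six results under the primary outcome, each at 5%, without saying which one decides. If all six are compared between arms with valid two-sided 5% tests and there is no true effect, the chance of at least one significant result is 26.5% under independence and about 21%, 16% and 11% at correlations of 0.5, 0.7 and 0.9. For the covariate associations, the supportable figure is 22.6% for five independent tests on one measure, and more if several items are used.

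The conclusion rests on reading sections 5.3 and 9 together to mean that each item is tested between arms. That is the natural reading, though the plan does not list its tests. The documents do not show that a false claim will be made, only that the stated rule leaves room for one.

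**What to change.** Change sections 5.3 and 9, and add a sentence to section 8.

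1. **Preference stays the main outcome.** Say which item or items measure it, and report it by arm as percentages with 95% confidence intervals. This suits the majority question in section 4. With 94 per group, the half-width at 50% is 1.96 × √(0.25/94) = 0.101, or about 10 percentage points.
2. **One between-arm significance test at 5%: item 1 (comfort).** It is the only item for which section 5.3 gives no arm-dependent wording. Annex 2 matches that wording; Annex 1 is not in the text available here and should be checked. If the sponsor prefers another item, it must be named and its recoding stated.
3. **Between-arm comparisons of items 2 to 6 are secondary.** Give confidence intervals only, or Holm-adjusted p-values after recoding the answers in both arms to a common direction, for or against a chaperone.
4. **Covariate associations are exploratory.** Say which item represents satisfaction.
5. **Limit the 5% sentence in section 9** to the item 1 test and, if p-values are kept, to the Holm-adjusted secondary family.
6. **In section 8, state that 31% against 14% does not give the power of the item 1 test.** Item 1 is a 0 to 10 score, and the documents give no standard deviation or target difference for it.

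No data collection changes. The cost is that a nominal p<0.05 on items 2 to 6 or on a covariate can no longer be claimed as a finding. The item 1 test is still run at the full 5%, but its power is not known from the documents.
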